Statistical Analysis Plan

Study Title: RSV Antibiotic Drivers and Resource-use (RADAR)

Document Date: May 10, 2025

NCT Number: Pending

Version: 1.0

1. Objectives

- To identify clinical, laboratory, and radiologic factors associated with antibiotic use in RSV-positive pediatric patients.
- To evaluate the impact of antibiotic use on hospital stay duration and treatment cost.

2. Study Design

This is a retrospective, single-center, observational comparative study conducted at [name] Uz Children's Hospital between April 2017 and April 2021. Children aged 1 to 24 months with laboratory-confirmed RSV-positive acute lower respiratory tract infections were included.

3. Study Population and Variables

- Population: RSV-positive children aged 1 to 24 months.
- Primary Variables: CRP, WBC, chest radiograph findings, presence of fever.

- Antibiotic-related Variables: Class/type of antibiotic used, timing of initiation, duration.
- Outcome Variables: Length of hospital stay, total cost of hospitalization.

4. Statistical Methods

- Statistical analyses were performed using SPSS Statistics v24.0.
- Categorical variables were compared using Pearson's Chi-square test or Fisher's exact test when appropriate.
- Continuous variables were analyzed using the Mann-Whitney U test or t-test based on normality assumptions.
- Multivariate logistic regression was used to identify independent predictors of antibiotic continuation.
- A p-value less than 0.05 was considered statistically significant.

5. Handling of Missing Data

Patients with incomplete clinical, laboratory, or radiologic data were excluded from the study and not included in the final analysis.

6. Cost Analysis

A micro-costing method was used based on hospital billing records. Costs were calculated in Turkish Lira (TRY) and then converted to U.S. Dollars (USD) using the average exchange rate between 2020 and 2022: 1 USD = 7.7784 TRY.

7. Ethical Considerations

The study was approved by the Ethics Committee of [name] Uz Children's Hospital (Approval No: 2021-634). All data were anonymized and handled in compliance with institutional and international ethical standards.

8. Document Control

- Author: [name]
- Affiliation: Ege University Faculty of Medicine, Department of Pediatric Cardiology
- Version: 1.0
- Date: May 10, 2025

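### Objective 2 has no comparison groups and no exposure window; grouping by any antibiotic use during the stay would make antibiotics appear to lengthen stay even with no effect

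*SAP*

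**What the plan says.** SAP section 1 gives two objectives; the second is "To evaluate the impact of antibiotic use on hospital stay duration and treatment cost". Section 2 states "This is a retrospective, single-center, observational comparative study" but not what is compared with what. Section 3 lists "Antibiotic-related Variables: Class/type of antibiotic used, timing of initiation, duration" and, separately, "Outcome Variables: Length of hospital stay, total cost of hospitalization". No rule turns the recorded start time into an exposure definition.

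For continuous outcomes section 4 offers only this: "Continuous variables were analyzed using the Mann-Whitney U test or t-test based on normality assumptions". Its one model is described as follows: "Multivariate logistic regression was used to identify independent predictors of antibiotic continuation". That model has neither stay nor cost as its outcome, and continuation is a different contrast from use. On cost, section 6 says "A micro-costing method was used based on hospital billing records" without saying whether billing lines are dated.

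No landmark, time-varying exposure or time-to-discharge method appears. The SAP also gives no sample size, length of stay, share treated or distribution of start times.

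**The concern.** At least two contrasts are open: any use against none, and continued against stopped. Neither has a time rule. Under any-use grouping, a child still in hospital on day 4 can yet become exposed, while a child discharged untreated on day 2 cannot. Long stays therefore move into the treated group whether or not antibiotics affect stay. This is time-dependent bias. It is separate from confounding by severity, and adjusting for admission covariates does not remove it.

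Both outcomes of one of the study's two objectives are affected: stay directly, and cost to the extent that it accrues by day. A positive finding would be read as antibiotics prolonging admission, and nothing in the SAP would let a reader judge whether it was an artefact.

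**Working it through.** The SAP has no figure to reproduce, so the check asks what an any-use comparison shows when antibiotics have no effect.

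**Inputs.** The significance level of 0.05 is from SAP section 4 (two-sided is assumed). Everything else is assumed: stay is gamma with shape 4 and mean 5 days (SD = 5/√4 = 2.5); N = 200; a share p0 starts at admission; the rest start at a constant rate r per day while in hospital; the test is Mann-Whitney.

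**Formula.** A child with stay L is never treated with probability (1 − p0)·exp(−rL). Hence:
- mean stay of never-treated children: m = 4/(0.8 + r)
- share ever treated: q = 1 − (1 − p0)·(0.8/(0.8 + r))⁴
- the overall mean is 5, so treated minus untreated = (5 − m)/q

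**Results.** Differences are from the formula. The last three columns are from null simulations, and ranges in the last column are across repeated runs.

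| p0 | r | m | q | Difference (days) | Treated who start after 48 h | Untreated at 24 h who start later | False positives |
|---|---|---|---|---|---|---|---|
| 0.4 | 0 | 5.00 | 0.40 | 0 | 0% | 0% | 5% |
| 0.4 | 0.03 | 4.82 | 0.4822 | 0.1807/0.4822 = +0.37 | 10% | 11% | 16–18% |
| 0.4 | 0.10 | 4.44 | 0.6254 | 0.5556/0.6254 = +0.89 | 19% | 31% | 67–69% |
| 0.2 | 0.10 | 4.44 | 0.5006 | 0.5556/0.5006 = +1.11 | 31% | 31% | 87–89% |
| 0.8 | 0.10 | 4.44 | 0.8751 | 0.5556/0.8751 = +0.63 | 5% | 31% | 22% |

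The share of treated children starting after 48 h does not determine the bias: 5% late gives +0.63 day in the last row, and 10% late gives +0.37 in the second. What matters is how many of the children untreated early go on to start, relative to stay, together with the share treated.

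**Does an early end to starts make it safe?** Not by itself.
- Starts end by 72 h: with p0 = 0.4 and r = 0.10, +0.11 day (6% false positives); with p0 = 0.4 and r = 0.5, +0.44 day (18%).
- Starts end by 48 h, most early starts at admission: 0.00 to +0.04 day (5%).
- Starts end by 48 h, with 40% of children destined to start uniformly over 0–48 h: about +0.12 day (6.5%) at mean 5 days and SD 2.5; +0.34 day (22%) at mean 4 days and coefficient of variation 0.6.

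**Other stay distributions and sample sizes.** Over SD 1.8 to 3.5, the 10%-late case gives +0.18 to +0.74 day and the 31%-late case +0.58 to +2.05. Over N = 100 to 400, false positives are 10–30% and 62–99% respectively.

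**Cost.** If all cost is daily, the relative excess follows stay: 0.3747/4.82 ≈ 8% (10% late) and 1.11/4.44 = 25% (31% late), with 13% and 77% false positives. If half of mean cost is a constant per admission, worth 5 days, these become 0.3747/(5 + 4.82) ≈ 4% and 1.11/(5 + 4.44) ≈ 12%. A constant does not change ranks, so the false-positive rates stay the same.

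**Landmark.** With exposure fixed at 24 h among children still in hospital, the difference is within 0.02 day and false positives are 4–6%. A calendar-day landmark is within 0.05 day (4.5–6.1%). Total cost in the same children differs by 0 to +1.2%.

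**Continued against stopped at 48 h** (all start at admission, 8% discharged before 48 h). If early discharges count as not continued, the difference is +0.61 to +1.23 days (49–91% false positives). If they are excluded, it is about 0.0 day (5%).

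**The case against.** The strongest reply is that the harm is conditional. It needs any-use grouping, which the SAP never states, and enough later starts, on which the SAP gives no data. With false-positive rates from 5% to about 89% across assumed inputs, the simulation shows a mechanism and not a magnitude for this study. That stands. No protocol text was available for this check, so groups or a window might be defined there; only the SAP omission is established.

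A second reply is that naming the groups and reporting start times closes the gap, and that a landmark changes the question from any use to early use. That stands in part. If essentially all starts are at admission, a landmark adds little, so it should depend on the start times. Otherwise reporting alone leaves a biased comparison in place.

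Three stronger readings are tempting. A reader might infer that the stay and cost results are biased, but the documents show neither the grouping nor the start times. A reader might infer that a continued/stopped contrast carries the same upward bias in any case, but it does so only if children discharged before the decision time count as not continued. A reader might infer that start time was ignored; the SAP lists it and merely states no use of it in defining exposure.

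**Conclusion.** The point holds as a gap in the SAP and should be fixed. One of two objectives has no defined contrast and no exposure window, and the only tests listed for its outcomes cannot handle exposure that begins during the stay. If grouping is by any use, the direction is clear: with no true effect, treated children appear to stay longer.

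The size is not fixed by the documents. With gamma stay (mean 5 days, SD 2.5) and 200 children, it runs from about 0 to +1.1 days, with 5% to about 89% false positives; a more variable stay widens this. It is about zero only if nearly all starts are at admission. Showing that starts ended by 48 h or 72 h would not by itself clear the analysis.

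**What to change.** 1. Name the groups compared for objective 2.
2. Report start times from admission, and the share of children untreated at 24 h who start later.
3. Unless essentially all starts are at admission, analyse stay and cost from a landmark. Exposed means started by 24 h, or by the end of the first calendar day if only dates are recorded. Include only children still in hospital then, and keep later starters as unexposed. Count stay from the landmark, and cost likewise, or use total cost in the same children if billing lines are undated. This may replace the any-use comparison or stand beside it.
4. If the contrast is continued against stopped, include only children still in hospital at the decision time.
5. Optionally, add a time-to-discharge model with time-varying antibiotic use as a sensitivity analysis.

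**Cost.** One exposure variable is re-derived from a field already listed. The methods are written in the past tense, so completed results may need re-analysis. Later starters dilute a real effect: they are 11% and 31% of the unexposed in the 10%-late and 31%-late cases. The question becomes early rather than any use. Children discharged before the landmark are lost, about 1% under the main assumptions and 6% with SD 3.5. Confounding by severity remains and needs separate adjustment.

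### The aim is the impact of antibiotic use on stay and cost, but the only stated tests are unadjusted, so group differences in age and admission year remain in the result

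*SAP*

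**What the plan says.** The second objective in SAP Section 1 is "To evaluate the impact of antibiotic use on hospital stay duration and treatment cost". Section 3 names the endpoints for it: "Outcome Variables: Length of hospital stay, total cost of hospitalization". It also lists "Primary Variables: CRP, WBC, chest radiograph findings, presence of fever", followed by the class, timing and duration of antibiotics.

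Age and calendar time occur only in the description of who was studied. Section 2 says "Children aged 1 to 24 months with laboratory-confirmed RSV-positive acute lower respiratory tract infections were included" and places the study "between April 2017 and April 2021". Neither age nor admission year is named in an analysis.

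Section 4 gives two methods that could bear on this. For continuous variables: "Continuous variables were analyzed using the Mann-Whitney U test or t-test based on normality assumptions". The one multivariable model has a different outcome: "Multivariate logistic regression was used to identify independent predictors of antibiotic continuation". No covariates are listed for it.

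Section 6 takes costs from billing records in TRY and converts them "using the average exchange rate between 2020 and 2022: 1 USD = 7.7784 TRY". It states no price year and no adjustment for the year of admission.

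**The concern.** The second objective is worded as a causal effect, but the stated tests only compare two groups as they happened to arise. In a retrospective study nobody assigned the antibiotics, so treated and untreated children may differ in ways that also affect stay and cost.

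Two such characteristics can be read off the design. Children of 1 month and of 24 months may differ both in how long they stay and in how often they receive antibiotics. Over four years, prescribing, discharge practice and prices may all have moved. If either characteristic is related both to antibiotic use and to the outcome, part of the reported difference is an age or calendar effect presented as the impact of antibiotics. With the analysis as written, a reader could not separate the two.

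**Working it through.** **Matching aim to method.** The SAP states no sample size, rate, mean or standard deviation, so there is no figure to reproduce. The first step is to set the sections side by side.

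| Item | SAP | Adjustment stated |
|---|---|---|
| Stay and cost by antibiotic use | Section 1, second objective; Section 4, Mann-Whitney U or t-test | None, and none is possible with these tests |
| Antibiotic continuation | Section 4, logistic regression | Covariates not listed |

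The logistic model cannot serve the second objective, because stay and cost are not its outcome.

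**Are the covariates to hand?** Age must be known to apply the 1 to 24 month criterion. Admission year is implied by the study window and the billing records, although Section 3 does not list it. Fever, CRP, WBC and radiograph are listed.

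**How large could the bias be?** All inputs below are assumptions. The true effect of antibiotics is set to zero, the groups are taken as treated and untreated, and the contrast is in means.

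*Stay, ignoring age.* Take two equal age groups with antibiotic shares y and o, and a mean stay that is d days longer in the first group.

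Spurious difference = d × [ y/(y+o) − (1−y)/(2−y−o) ]

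- y = o, any d: 0 days.
- y = 0.6, o = 0.5, d = 0.5: 0.5 × (0.545 − 0.444) = 0.05 day.
- y = 0.6, o = 0.4, d = 2: 2 × (0.6 − 0.4) = 0.40 day.
- y = 0.7, o = 0.4, d = 2: 2 × (0.636 − 0.333) = 0.61 day.

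*Cost, ignoring year.* Take four equal years, an antibiotic share p falling linearly from 0.60 to 0.40 (0.600, 0.533, 0.467, 0.400), and a cost c that grows by a fixed percentage each year.

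Spurious ratio = [Σpc/Σp] / [Σ(1−p)c/Σ(1−p)]

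- 10% growth (c = 1, 1.1, 1.21, 1.331): (2.2837/2) / (2.3573/2) = 0.969, or −3.1%.
- 15% growth: 2.4389/2.5545 = 0.955, or −4.5%.
- 20% growth (c = 1, 1.2, 1.44, 1.728): 2.6032/2.7648 = 0.942, or −5.8%.
- Other drifts: a share falling from 60% to 50% with 10% growth gives 0.984; from 70% to 40% with 20% growth gives 0.913.
- Constant share or constant cost: ratio 1.00.

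The sign matters. In this scenario the bias makes treated children look cheaper, so it would hide an excess cost.

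**What adjustment for age and year leaves behind.** Suppose severity is unrelated to age and year, half the children are severe, and severe children stay 2 days longer. The stay formula then applies with severity in place of age.

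- Antibiotic shares of 70% and 50%: 2 × (0.583 − 0.375) = 0.42 day.
- Antibiotic shares of 80% and 40%: 2 × (0.667 − 0.250) = 0.83 day.

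Adjusting for age and year does not touch this, so the model also needs whatever severity markers are available.

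**The case against.** **The sizes are invented.** This stands. No figure in the documents supports an age gradient, a drift in prescribing or price growth, and the bias is exactly zero under inputs that the documents equally allow. The calculations show what the planned tests would let through, not what happened.

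**Age and year may not be the main problem.** This also stands. Confounding by severity could be larger, and a model adjusted for age and year alone might lend false assurance to a claim of impact. A reader might infer that adding these two terms would remove the confounding. It would deal only with confounding by age and year, and only if both are modelled adequately.

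**The logistic model may already include age and year.** A reader might infer that the predictor odds ratios omit both. The SAP does not show that. The covariates are unlisted, the Section 3 list is not said to be complete, and the clinical factors of the first objective could include age. The point therefore does not rest on the logistic model.

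**The exchange rate is not the culprit.** A reader might infer that converting four years of costs at one rate distorts the comparison. Dividing both group means by 7.7784 leaves their ratio unchanged. What could distort it is movement in TRY prices across years, and then only if costs were taken at the prices of the admission year, which Section 6 does not say.

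**Adjustment is not free.** Correct. Extra terms use degrees of freedom, and no sample size is given to judge whether that matters. Section 7 says the data were anonymized, and whether admission dates remain in the analysis file is not stated.

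**The protocol may say more.** Its text was not available for this check, so the point concerns the SAP alone.

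**Conclusion.** The point holds for length of stay and cost. The SAP's aim for these outcomes is an impact, its stated methods are unadjusted tests, and its only regression answers a different question. Followed as written, the comparison carries any imbalance in age and admission year into the result.

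The size is unknown. With no true effect and the assumed inputs, the spurious stay difference runs from nil to about 0.6 day. With antibiotic use falling from 60% to 40% and yearly price growth of 10% to 20%, treated children look about 3% to 6% cheaper; milder or steeper assumptions give about 2% to 9%, and no drift in either gives none. These figures concern means; a Mann-Whitney test is open to the same confounding, but its result is not in days or currency.

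The documents do not show that the bias is material, that it inflates the cost of treatment, or that the logistic model leaves out age and year.

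**What to change.** In SAP Section 4, add a regression of length of stay and one of cost on antibiotic use, with a form suited to skewed outcomes (for example, a log-link or gamma model). Adjust both for age in months, admission year, fever, CRP, WBC and radiograph findings. State that the last four are values from before the antibiotic decision, since the SAP gives no time point for them. Make these the main analysis and keep the unadjusted tests as descriptive. Add age and admission year to Section 3, and state in Section 6 which year's prices the costs reflect.

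If residual confounding by severity cannot be excluded, report the result as an association and reword the second objective to match.

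Listing the logistic model's covariates, with age and year among them, is advisable but separate.

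The cost is SAP wording, a re-analysis and some degrees of freedom. The window touches five calendar years, so year as indicators takes 4 terms. With 1 for linear age and 1 for each of the four markers, that makes 4 + 1 + 4 = 9 beyond the antibiotic term. Year as a linear term reduces this to 1 + 1 + 4 = 6; a curved age term adds a little. No new data should be needed: the markers are listed, age is known from eligibility, and only the year of admission is required, not the date.

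### The SAP sets out to measure the impact of antibiotics on stay and cost but plans no adjusted analysis of either outcome

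*SAP*

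**What the plan says.** SAP section 1 has two objectives. The second reads: "To evaluate the impact of antibiotic use on hospital stay duration and treatment cost". Section 2 describes the design: "This is a retrospective, single-center, observational comparative study". Section 3 names the two outcomes: "Outcome Variables: Length of hospital stay, total cost of hospitalization".

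Section 4 lists the methods:

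- chi-square or Fisher tests for categorical variables;
- for continuous variables, "Continuous variables were analyzed using the Mann-Whitney U test or t-test based on normality assumptions";
- one multivariable model: "Multivariate logistic regression was used to identify independent predictors of antibiotic continuation".

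Section 4 does not say which method serves the second objective, or which groups of children are compared for it. Section 6 deals only with costing from billing records and conversion to US dollars.

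**The concern.** Antibiotics in this cohort were given for reasons. The first objective is to find the clinical, laboratory and radiologic factors associated with their use, so the plan itself anticipates that treated and untreated children differ. If those factors also relate to stay or cost, a crude comparison mixes any effect of the antibiotic with the reasons for prescribing it. The SAP does not state that second link, and nothing in it fixes the size or direction of the bias.

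A second, conditional problem is timing. The SAP does not say whether children are grouped as ever versus never treated. If they are, a child who stays longer has more days on which an antibiotic can be started. That produces a difference in stay even without confounding, and covariate adjustment does not remove it.

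This is one of only two objectives. A reader given a significant difference could not tell an antibiotic effect from confounding by indication.

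**Working it through.** **1. Matching outcomes to methods.** There is no SAP figure to reproduce, because the point is an absent analysis. I looked through every section for a model with stay or cost as the dependent variable, and for any matching, weighting or stratification.

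| SAP section | Bearing on stay and cost |
|---|---|
| 3 | Names them as outcomes |
| 4, categorical tests | Do not fit continuous outcomes |
| 4, Mann-Whitney or t-test | Fit, but are unadjusted two-group comparisons |
| 4, logistic model | Different outcome (antibiotic continuation) |
| 5 | Exclusion of incomplete records only |
| 6 | Costing and currency only |

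The two-group tests are therefore the only candidates. If they are not meant for these outcomes, the objective has no analysis at all.

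**2. Illustration of size.** The SAP gives no sample size, mean stay, SD, cost or prescribing rate, so every input here is assumed. Severity S ~ N(0,1); logit P(antibiotic) = a + bS; log outcome = c + gS + error. There is no antibiotic effect. Half the children are treated, mean stay is 5 days, and the residual log-SD is 0.4 for stay and 0.6 for cost.

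- b = 0.5, 1.0, 1.5 gives odds ratios per SD of exp(b) = 1.65, 2.7, 4.5.
- g = 0.1, 0.2, 0.3 gives exp(g) − 1 = 11%, 22%, 35% longer stay per SD.

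Crude results (3,000,000 simulated children for the differences; 10,000 studies for each rejection rate):

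| | Weak | Central | Strong |
|---|---|---|---|
| Spurious ratio, treated/untreated | 1.048 | 1.179 | 1.375 |
| Spurious difference, days | 0.236 | 0.822 | 1.579 |
| Ratio with g negative | 0.955 | 0.847 | 0.727 |
| Mann-Whitney false positives, stay, N = 100/200/400 | 8.6/12.3/20.0% | 43.6/72.8/95.2% | 88.9/99.7/100% |
| Same, cost | 6.8/8.2/11.7% | 24.1/44.1/72.2% | 64.8/91.1/99.8% |

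Consistency check: with half treated and an overall mean of 5, the difference is 5(r − 1)/[(1 + r)/2]. For r = 1.179 this is 5 × 0.179/1.0895 = 0.82 day, and for r = 1.375 it is 5 × 0.375/1.1875 = 1.58 days.

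With either link at zero, rejection is 4.7–5.1%, as it should be. In the central case the ratio stays at 1.18 with 30%, 50% or 70% treated. At N = 200 the false-positive rate for stay reaches 10% once the spurious ratio is about 1.04, which is 5 × 0.04/1.02 = 0.2 day.

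**3. What adjustment achieves.** Groups are formed by antibiotic start on admission (about 42%), with later starts at 5% per day (54% ever treated). Ratios come from a log-link gamma GLM on 1,000,000 children; rejection at N = 200 comes from a log-linear model over 1,500 studies.

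| Severity variance captured by covariates | Weak | Central | Strong |
|---|---|---|---|
| Half: ratio (false positives) | 1.024 (6.8%) | 1.095 (30.7%) | 1.204 (77.8%) |
| All: ratio (false positives) | 0.999 (4.1%) | 0.999 (5.1%) | 0.999 (5.8%) |

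On the log scale, half capture leaves roughly 51%, 55% and 58% of the crude bias: ln 1.024/ln 1.048, ln 1.095/ln 1.179 and ln 1.204/ln 1.375. This comparison is approximate, because the treated share differs between the two settings.

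**4. Late starts, only if grouping is ever versus never.** With no confounding, an admission share of 0.3–0.5 and late starts of 2–10% per day, the spurious difference is 0.16 to 0.68 day. At 5% per day with confounding present and fully captured, the ever-versus-never ratio is still about 1.08, against 1.00 for admission-start groups.

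**The case against.** The strongest reply is that *impact* is loose wording. The design is openly observational, the SAP claims no causal estimate, and an unadjusted comparison is legitimate if labelled as one. On that view one sentence in section 1 needs changing. This stands in part: rewording is a sufficient minimum. But the SAP carries no such label and no caveat about confounding, so some change is needed either way.

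Second, the illustration assumes confounding and then finds it. The SAP never calls CRP, WBC, radiograph findings or fever markers of severity. This also stands: the figures show how small a link would matter, not that it exists here.

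Third, adjustment is imperfect. With half the severity variance captured, the central case still gives a ratio of 1.095 and 31% false positives. That is a reason to state the limitation and drop causal wording even after adjusting; it does not favour the crude test.

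Fourth, the logistic model's outcome suggests that the intended contrast may be continued versus stopped antibiotics, and admission-start grouping would then change the question. That is fair. The sponsor should state the exposure first and set the index time to match.

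Finally, the protocol might contain an adjusted analysis. It was not available for this check, so the point is limited to the SAP.

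**Conclusion.** The concern holds for the SAP. The absence of any adjusted analysis of stay or cost is plain from the text, and confidence in that is high. Followed as written, section 4 yields a crude comparison under a causally worded objective, and this should be corrected before results for that objective are reported.

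The size of any bias in this study cannot be calculated from the SAP. Under the assumptions above, the spurious stay ratio runs from 0.73 to 1.37, and it disappears if either severity link is absent. The late-start point is secondary and depends on a grouping that the SAP does not specify.

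**What to change.** Amend section 4, with a date and a post hoc label, since the section is written in the past tense.

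1. State the exposure contrast for the second objective and define the groups at a common index time. Started on admission or not is one example.
2. Make the main analysis of each outcome a multivariable model, for example a log-link gamma GLM. Include antibiotic group, CRP, WBC, radiograph finding and fever, all measured at admission, plus age and admission date if recorded.
3. Report adjusted ratios or differences with 95% CIs, and keep the crude tests as descriptive.
4. Replace *impact* with *adjusted association*, and state that residual confounding by unmeasured severity may be substantial.
5. State whether total cost includes the antibiotics themselves.
6. If ever-versus-never groups are used, add a sensitivity analysis based on time of initiation.

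If no model is added, reword the second objective as a descriptive, unadjusted comparison.

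**Cost.** This needs SAP wording and two models. Section 3 already lists the main covariates ("Primary Variables: CRP, WBC, chest radiograph findings, presence of fever") and the timing of initiation. Section 5 already excludes incomplete records, so few or no further children should be lost. The SAP does not say whether the values are from admission, which may need record review; admission date is not listed.

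Intervals widened by 0–2% in the simulation with one covariate index, and could widen more with several covariates. The reported difference may shrink. Admission-start grouping leaves later starters in the comparison group, which dilutes a true effect: in the central case (54 − 42)/(100 − 42), about 21% of that group.

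### Objective 1 is about antibiotic use, but the SAP's only multivariable model takes antibiotic continuation as its outcome

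*SAP*

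**What the plan says.** Section 1 of the SAP gives the first objective as "To identify clinical, laboratory, and radiologic factors associated with antibiotic use in RSV-positive pediatric patients". Antibiotic use is the outcome there.

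The study group is described without any restriction to treated children. Section 2 says "Children aged 1 to 24 months with laboratory-confirmed RSV-positive acute lower respiratory tract infections were included", and section 3 says "Population: RSV-positive children aged 1 to 24 months".

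Section 3 lists three groups of variables. The antibiotic group reads "Antibiotic-related Variables: Class/type of antibiotic used, timing of initiation, duration". The outcome group holds how long the child stayed and what the admission cost. The remaining group, which the SAP treats as its main variables, reads "Primary Variables: CRP, WBC, chest radiograph findings, presence of fever".

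Section 4 names chi-square or Fisher's exact tests for categorical variables, Mann-Whitney or t-tests for continuous ones, and one multivariable method: "Multivariate logistic regression was used to identify independent predictors of antibiotic continuation". Continuation is mentioned nowhere else in the SAP, and no covariate list is given for the model.

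**The concern.** A child must have started an antibiotic before anyone can decide to continue it. On the ordinary meaning of the words, use is a yes/no outcome in every included child, and continuation is a yes/no outcome in the children who started. The factors that lead a clinician to start need not be those that lead a clinician to carry on.

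If the model was fitted as written, its adjusted odds ratios describe the second decision, and the factors associated with the first have been compared without adjustment. CRP, WBC, radiograph findings and fever are plausibly correlated with one another, so unadjusted tests cannot separate their contributions. A reader who sees adjusted odds ratios in a study whose stated aim is about use may take them as results about use. If the model was in fact fitted to use, the analysis suits the objective and only the name of its outcome is wrong.

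**Working it through.** No figure in the SAP can be reproduced here: it gives no sample size, event count or effect size. The check is a comparison of the text.

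1. **Outcome in the objective (section 1):** antibiotic use.
2. **Outcome in the model (section 4):** antibiotic continuation.
3. **Population (sections 2 and 3):** all RSV-positive children aged 1 to 24 months. Continuation, read plainly, needs the subset who started, and the SAP names no such subset.
4. **Variables (section 3):** neither use (yes/no) nor continuation is itemised. Use can be derived, because a child with no antibiotic class and no start time is untreated. Continuation cannot be derived from the SAP alone, because no rule turns duration into a yes/no variable.
5. **Other methods (section 4):** every other test named is unadjusted.

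The two readings are therefore:
- Continuation means continuation: objective 1 has unadjusted tests only, and the adjusted model addresses another question.
- Continuation means use: objective 1 has its adjusted model, under the wrong name.

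An illustration with **assumed counts, not study data**, shows why the choice is not cosmetic. Take 1,000 children, 400 with some factor and 600 without. Suppose 280 of the 400 and 240 of the 600 start an antibiotic. The odds ratio for use is (280/120)/(240/360) = 3.50.

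| Assumed number continuing, with / without the factor | Starters only | All children, untreated coded as not continued |
|---|---|---|
| 140 of 280 / 120 of 240 | (140/140)/(120/120) = 1.00 | (140/260)/(120/480) = 2.15 |
| 224 of 280 / 96 of 240 | (224/56)/(96/144) = 6.00 | (224/176)/(96/504) = 6.68 |

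With the same odds ratio for use, the odds ratio for continuation can be lower or higher, and it also depends on how untreated children are handled. These are crude odds ratios from invented inputs. They show that the two outcomes are not interchangeable and nothing more.

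**The case against.** The strongest reply is that objective 1 asks only for association. Unadjusted tests do address association, and the SAP attaches the word independent to continuation alone. A model of continuation can properly sit beside unadjusted comparisons for use. This stands in part: objective 1 is not left without any analysis. But the adjusted model is the more informative analysis in section 4, and the SAP does not say that it serves a question other than the stated one.

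A second reply is that continuation is loose wording for use. That may be so, and the remedy is then a corrected word.

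A third is that the protocol may define continuation, its time point and its denominator. The protocol text was not available for this review, so a reader should not infer that the plan as a whole leaves the term undefined. What can be said is that the SAP neither defines it nor points to a definition. A definition elsewhere would not remove the mismatch with objective 1.

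A reader might also extend the point to the second objective, "To evaluate the impact of antibiotic use on hospital stay duration and treatment cost". The documents do not support that. Use is the exposure there, and the outcomes are length of stay and cost, so no logistic model of use or of continuation would serve that objective. Its unadjusted comparisons are a separate matter.

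**Conclusion.** The mismatch between objective 1 and the outcome of the only multivariable model is real on the face of the SAP, and should be fixed. It rests on the plain meaning of continuation and on the SAP text alone. Confidence is medium, because the wording may be a slip and the protocol could not be consulted.

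It is tempting to conclude that the reported odds ratios are biased for use, or weaker than they should be. The documents give no basis for either. With no rates or effect sizes, the size and direction of any difference in this study are unknown, and the assumed counts are not evidence about it. Nor does the point invalidate the study: it limits what the adjusted result can be said to show.

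**What to change.** For objective 1, make antibiotic use (yes/no) in all included children the outcome of the multivariable logistic model, list that outcome in section 3, and state what counts as use. CRP, WBC, chest radiograph findings and fever should be among the predictors. They should not be the only ones, since section 3 does not present them as the model's covariate list. Other baseline factors already collected belong with them, such as age, which must be known because eligibility depends on it.

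If continuation was a slip for use, correct the word in section 4. If it was intended, keep it as a separate, labelled model restricted to children who started antibiotics, state or cite its definition and time point, and limit its conclusions to those children.

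The cost is SAP wording and at most one additional model on data already held. The SAP is dated May 10, 2025 and describes the regression in the past tense, on data from April 2017 to April 2021, so a use model added now should be labelled post hoc. Renaming a model that was already fitted to use adds no new analysis.
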